11.2. The Number of Participants

75 patients will be recruited to the study. All participants will be invited to optionally participate in the MRI substudy of whom at least 30 will be imaged on sildenafil and placebo alone, and up to 30 on all three treatments. Participants who leave the study before taking any trial medication will be replaced. Participants unable to tolerate the MRI scan will continue in the main study, but will be replaced by new recruitment to the substudy, where necessary.

11.3. The Level of Statistical Significance

At a power level of 0.9, with a 2-sided significance of 5%, a clinically relevant 0.12 unit change in pulsatility index (equivalent to a ~20% difference in risk of recurrent stroke), and conservatively allowing for a standard deviation of differences in PI between repeated measures of 0.2, gives an estimated minimum sample size of 32 patients (paired t-test). Allowing for a 15% drop-out rate, 38 patients would be required. A sample size of 66 achieves 90% power to detect the non-inferiority of sildenafil c.f. cilostazol using a non-inferiority margin of 0.08 (and mean of paired differences 0) at $\alpha=0.025$ (for a 95% CI) with a within-subject variance of 0.02 (equivalent to a SD of differences 0..^{23,24} This equates to 75 patients in total with a 12% drop out rate.

A two-sided 5% significance level will be used for all hypothesis tests.

11.4. Criteria for the Termination of the Study

A Data and Safety Monitoring Board will be established. They will review the data after 30 patients have been recruited to the study, or 12 months after the first visit of the first patient (whichever is sooner), or at the request of the sponsor or CI. If a decision to terminate the study is contemplated, this will be discussed with the CI and the sponsor prior to a final decision being made.

The advisory recruitment threshold is set at projected recruitment of <35 patients in 2 years, allowing for any delays resulting from the COVID-19 pandemic. No threshold is defined for efficacy for study cessation. Any statistically significant excess of SAEs in the treatment arm, or occurrence of unexpected treatment-related SAEs of sufficient severity (in the view of the DSMB), may also result in early cessation of the study. If after 12 months the recruitment falls below the rate expected to complete the study in 3 years, allowing for delays due to the COVID-19 outbreak, the overall study size can be reduced to 50 participants. Any data collected to that date, including on cilostazol, will be retained and analysed according to the original study plan. An interim statistical analysis plan will be signed off prior to the interim analyses.

11.5. Procedure for Accounting for Missing, Unused, and Spurious Data.

All physiological data will be reviewed and cleaned by automated and manual processes to reduce artefactual data. Data will be defined as artefactual or missing. The statistical analysis plan will describe the procedure for accounting for missing or spurious data. The completeness and correctness of the data will be monitored as per the monitoring plan

11.6. Inclusion in Analysis

All possible data will be used on an intention-to-treat basis, but where patient withdrawal results in missing data, the final primary analysis will only include patients where primary outcome data is available (Gosling's MCA-PI).

11.7. Procedures for Reporting any Deviation(s) from the Original Statistical Plan

All deviations from the statistical analysis plan for the study will be reported in the final report of the study.

12. DATA MANAGEMENT

12.1. Source Data

Source documents are where data are first recorded, and from which participants' CRF data are obtained. These include, but are not limited to, hospital records (from which medical history and previous and concurrent medication may be summarised into the CRF), clinical and office charts, laboratory and pharmacy records, diaries, microfiches, radiographs, and correspondence.

CRF entries will be considered source data if the CRF is the site of the original recording (e.g. there is no other written or electronic record of data). All documents will be stored safely in confidential conditions. On all study-specific documents, other than the signed consent, the participant will be referred to by the study participant number/code, not by name.

12.2. Access to Data

Direct access will be granted to authorised representatives from the Sponsor, host institution and the regulatory authorities to permit study-related monitoring, audits and inspections.

12.3. Data Recording and Record Keeping

All study data will be entered and stored on paper CRFs. The participants will be identified by a unique study specific number and/or code in any database. The name and any other identifying detail will NOT be included in any study data electronic file.

13. QUALITY ASSURANCE PROCEDURES

The study will be conducted in accordance with the current approved protocol, GCP, relevant regulations and standard operating procedures.

Regular monitoring will be performed according to GCP. Data will be evaluated for compliance with the protocol and accuracy in relation to source documents. Following written standard operating procedures, the monitors will verify that the clinical study is conducted and data are generated, documented and reported in compliance with the protocol, GCP and the applicable regulatory requirements.

14. ETHICAL AND REGULATORY CONSIDERATIONS

14.1. Declaration of Helsinki

The Investigator will ensure that this study is conducted in accordance with the principles of the Declaration of Helsinki.

14.2. Guidelines for Good Clinical Practice

The Investigator will ensure that this study is conducted in accordance with relevant regulations and with Good Clinical Practice.

14.3. Approvals

The protocol, informed consent form, participant information sheet and any proposed advertising material will be submitted to an appropriate Research Ethics Committee (REC), HRA (where required), and host institution(s) for written approval.

The Investigator will submit and, where necessary, obtain approval from the above parties for all substantial amendments to the original approved documents.

14.4. Reporting

The CI shall submit once a year throughout the clinical study, or on request, an Annual Progress Report to the REC, HRA (where required), host organisation and Sponsor. In addition, an End of Study notification and final report will be submitted to the MHRA, the REC, host organisation and Sponsor.

14.5. Participant Confidentiality

The study staff will ensure that the participants' anonymity is maintained. The participants will be identified only by a participant ID number on all study documents and any electronic database, with the exception of the CRF, where participant initials may be added. All documents will be stored securely and only accessible by study staff and authorised personnel. The study will comply with the Data Protection Act, which requires data to be anonymised as soon as it is practical to do so, and the General Data Protection Regulation to ensure transparency and confidentiality of data use.

14.6. Expenses and Benefits

Reasonable travel expenses for any visits additional to normal care will be reimbursed on production of receipts, or a mileage allowance provided as appropriate.

14.7. Other Ethical Considerations

Potential incidental findings detected on brain imaging will be reviewed by the study Chief Investigator ([name]). If deemed to be potentially clinically significant, this will be reviewed under the fMRIB SOP for incidental findings, including referral to an independent neurologist ([name]), review by a neuroradiologist if indicated and an independent clinical appointment arranged for the patient with the independent neurologist to discuss the findings and any implications. If this process is required, the chief investigator will inform the participant that an incidental finding has been identified on their brain scan and that they will have the opportunity to discuss this with an independent neurologist if they wish.

Incidental findings identified on physiological testing or clinical examination will be reviewed by the study chief investigator. If any clinical action needs to be taken, the chief investigator will discuss this with the participant and contact the participant's GP to initiate an appropriate clinical response.

If patients lose capacity during the study, they will be withdrawn from the study and their GP will be informed. If this occurs as a result of study procedures or treatments, they will be followed up by the study

team until resolution of the adverse event or until they are clinically stable. Data collected up to the point of their withdrawal from the study will be retained.

Finally, male participants will be asked if they have a deformity of the penis which is a contraindication to use of sildenafil due to an increased risk of priapism. This is a personal question but will be asked sensitively by an experienced physician.

15. FINANCE AND INSURANCE

15.1. Funding

The study is funded through a Wellcome Trust Clinical Research Career Development Fellowship, held by the Chief Investigator (AW).

15.2. Insurance

The University has a specialist insurance policy in place which would operate in the event of any participant suffering harm as a result of their involvement in the research (Newline Underwriting Management Ltd, at Lloyd's of London). NHS indemnity operates in respect of the clinical treatment that is provided.

16. PUBLICATION POLICY

Any publications resulting from this study will be authored by the chief investigator and any additional study physicians recruited to the study in the future. In addition, any substantive contribution in recruiting and monitoring patients at non-core sites (Reading, High Wycombe, Swindon) will be recognised by authorship / acknowledgement, depending upon the level of involvement. There is no expectation that this study will generate intellectual property.

18. APPENDIX D: AMENDMENT HISTORY

Amendment No.	Protocol Version No.	Date issued	Author(s) of changes	Details of Changes made
1	2.0	14 th April 2020	[name]	See document 'OxHARP Amendment 1_14_4_20.docx'

Protocol amendments must be submitted to the Sponsor for approval prior to submission to the REC committee or MHRA.

1.1 Purpose and scope of the plan

This document details the proposed analysis for the main paper(s) and final study report from the Wellcome Trust-funded *Oxford Haemodynamic Adaptation to Reduce Pulsatility Trial: Randomised, placebo controlled, double-blind crossover study of effects of sildenafil on cerebral arterial pulsatility in patients with cryptogenic or lacunar stroke and small vessel disease*. The results reported in these papers should follow the strategy set out here which adheres to the guidelines for the content of a statistical analysis plan¹. Any subsequent analyses of a more exploratory nature will not be bound by this strategy though they are expected to follow the broad principles described in this document.

Suggestions for subsequent analyses by journal editors or referees will be considered carefully and carried out as far as possible in line with the principles of this analysis plan. Any deviations from the statistical analysis plan will be described and justified in the final report of the trial.

This statistical analysis plan is based on the latest version of the protocol.

1.2 Overview of the trial

Chronic injury to the small vessels of the brain ('small vessel disease') is associated with acute stroke, progressive cognitive decline, late-onset refractory depression, functional impairment in daily living and increased mortality. This study will investigate whether vasodilating medications are good candidates to reduce the progression of small vessel disease. The physiological effect of sildenafil, a phosphodiesterase 5 (PDE5) inhibitor, on cerebral arterial pulsatility will be tested, with secondary assessment of effects on cerebrovascular endothelial function. Participants will be recovered patients with a previous cryptogenic or lacunar stroke or probable TIA requiring treatment, and mild-moderate small vessel disease. Taking this population will allow assessment of effects on cerebrovascular physiology in the presence of small vessel injury, but prior to establishment of likely irreversible changes. Participants will also receive cilostazol (a PDE3 inhibitor), an active control, to compare the relative effect of PDE5 inhibition and PDE3 inhibition on cerebrovascular haemodynamics.

1.3 Trial objectives

Primary objective

To assess whether 3 weeks of treatment with sildenafil (a PDE5 inhibitor) reduces cerebral arterial pulsatility on transcranial ultrasound, compared to placebo in patients with chronic vascular injury to the brain (small vessel disease).

Secondary objectives

1. To assess whether 3 weeks of treatment with sildenafil alters cerebral arterial reactivity to carbon dioxide on transcranial ultrasound, compared to placebo (The null hypothesis is that there is no difference in the mean change between the sildenafil and placebo groups)
2. To assess whether 3 weeks of treatment with sildenafil has non-inferior effects on cerebral arterial pulsatility and reactivity to carbon dioxide on transcranial ultrasound, compared to cilostazol (The null hypothesis is that sildenafil is unacceptably inferior to cilostazol i.e. the change in mean flow velocity upon CO₂ challenge with sildenafil differs from that with cilostazol by more than the non-inferiority margin Δ).

3. To assess whether 3 weeks of treatment with sildenafil or cilostazol increases cerebral arterial reactivity to carbon dioxide on MRI, compared to placebo, in normal appearing white matter and within white matter hyperintensities.

Tertiary objectives (exploratory and mechanistic)

1. To assess whether 3 weeks of treatment with sildenafil or cilostazol increases cerebral arterial reactivity to carbon dioxide on MRI, compared to placebo, for all defined cerebral tissue type (all white matter and grey matter) and on a voxel-wise basis.
2. To assess whether there is an increased incidence of adverse events or serious adverse events with sildenafil or cilostazol compared to placebo.
3. To assess whether 3 weeks of treatment with sildenafil or cilostazol affects the following physiological parameters, compared to placebo:
 - a) Systolic and diastolic blood pressure on 1 week of home blood pressure monitoring
 - b) Arterial stiffness (carotid-femoral pulse wave velocity)
 - c) Aortic pulse pressure
 - d) Beat-to-beat and day-to-day variability in systolic blood pressure
 - e) Flow mediated slowing
 - f) Resting state cerebral autoregulation (transfer function analysis derived gain, phase and coherence between beat-to-beat blood pressure and cerebral blood flow velocity during a minimum of 5 minutes of monitoring).
 - g) Alternative estimates of CVR (change in mean flow velocity per unit change in etCO₂) determined during hyperventilation, 4% CO₂ and 6% CO₂, each versus air.

2. Trial design

OxHARP is a randomised, placebo and actively controlled, three-arm double-blind (patient and clinician), assessor-blinded crossover trial. Using random allocation, participants will have three weeks of treatment with each of the following: sildenafil (25mg TDS, titrated to 50mg TDS after one week), placebo (one tablet TDS, titrated to 2 tablets after one week), cilostazol (50mg BD, titrated to 100mg BD after one week, with midday placebo). Following each treatment period, participants will undergo a clinical and physiological assessment, followed by at least one week washout before starting the next treatment. A subgroup of participants will undergo MRI imaging following sildenafil and placebo treatments to assess arterial pulsatility on MRI and cerebrovascular reactivity, and a further subgroup will undergo MRI on all three treatments. The primary objective will be assessed using a superiority hypothesis testing framework and a non-inferiority framework will be used for the secondary objective.

2.1 Outcome measures

A detailed description of the physiological assessment measures is provided in the protocol (sections 8.5 & 8.6)

2.1.1 Primary outcome measure

Change in Gosling's middle cerebral arterial pulsatility index (MCA-PI) from baseline to end of treatment (after three weeks), utilising the visually-assessed, better quality transcranial Doppler TCD recording with a handheld probe, defined by blinded assessor.

MCA-PI will be calculated according to the formula below for each middle cerebral artery from the peak systolic velocity and end-diastolic velocity determined by operator. PSV and EDV will be determined from manually determined values across the average of three beats, during 2 recordings.

MCA-PI will be calculated for each recording, and an average of two recordings used to determine the MCA-PI for that cerebral hemisphere. 2 blinded reviewers will independently review the recordings to identify recordings that should be re-analysed or excluded due to poor quality resulting in an inaccurate value of MCA-PI. Each reviewer will also identify which side provides a better quality recording. Where no difference in recording quality between sides is evident either from visual blinded assessment or by an inconsistency in PSV of >10 cm/s, an average of the two sides will be used for the primary value of MCA-PI, otherwise the side with the better blinded quality assessment or the side with the high PSV will be used. If the PSV measured during the first 15s of the 5 minutes of TCD monitoring exceeds the PSV estimated with the hand-held probe by >10 cm/s, this period will be used to estimate MCA-PI instead.

Gosling's MCA-PI = (peak systolic velocity – end diastolic velocity)/(mean flow velocity), where flow velocity is measured in cm/s.

2.1.2 Secondary outcome measures

Percentage change in middle cerebral artery mean flow velocity per mmHg increase in concurrent end-tidal CO₂ on TCD ultrasound will be estimated by the unstandardized beta-coefficient from an unadjusted linear regression between the end-tidal CO₂ and MCA mean velocity during inhalation of 90 seconds of air, 2 minutes 4% CO₂, 2 minutes of air and 2 minutes of 6% CO₂, assessed following three weeks of treatment ('CVR'). Prior to linear regression procedure, any time delay between the etCO₂ waveform and the MCA MV will be estimated by the maximum R value in a standard cross-correlation analysis, and the etCO₂ trace shifted by this value. The side of insonation will be selected by the same quality assurance method as for MCA-PI. A sensitivity analysis will be performed using the standardised beta-coefficients for increase in blood flow velocity per increase in end-tidal CO₂.

Cerebrovascular reactivity on MRI during inhalation of air or 6% CO₂ in 2 minutes intervals (boxcar design) will be estimated as the percentage change in BOLD signal per mmHg change in end-tidal CO₂, estimated from the beta-coefficient of a general linear model between each voxel time-series and a phase-shifted etCO₂ trace shifted by the time-delay with the maximum r^2 by cross-correlation (FSL FEAT). The core ROIs will be normal-appearing white matter voxels and white matter voxels within a white matter hyperintensity on a 'BIANCA' mask. Secondary ROIs include total white matter, white matter hyperintensities and superficial and deep grey matter masks. BOLD scans will be preprocessed with the fMRI Expert Analysis Tool from the fMRI software library (FEAT), including field-map based bias field correction, high pass temporal filtering (300s cycle length), motion correction (MCFLIRT) and registration to structural (FLIRT) and standard space (FNIRT).

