monitoring insonation of the middle cerebral artery will be established with 2 probes held to the head a with a comfortable headset, with spectra acquired by a DWL Doppler Box to a dedicated laptop. This waveform will be acquired over 10 minutes with concurrent heart rate and blood pressure monitoring (see below). End-tidal carbon dioxide monitoring will be performed with AD Instruments Gas Analyser ML206. All waveforms will be simultaneously acquired with a AD Instruments Powerlab 8/35.

Continuous non-invasive blood pressure monitoring

Continuous ECG and BP will be recorded using a Finometer (BP monitor which allows continuous non-invasive assessment of finger arterial pressure). After a period of at least 5 minutes of rest and after achievement of a satisfactory BP signal from the monitor and the stabilization of BP at the same level, recordings will be performed for up to 10 minutes (minimum 5 minutes). The outputs from the Finometer and simultaneous surface ECG recordings will be analysed to estimate cerebral autoregulation and transmission of arterial pulsatility using in-house analysis programs written in Matlab, according to both sequential and spectral methods. The system will be allowed to establish a stable internal calibration before this function is turned off for the monitoring period. A standard brachial blood pressure will be obtained twice with a calibrated device (A&D UA-767 BT) from the contralateral arm twice, and the Finometer trace calibrated to this reading by 2 point calibration.

Cerebral Autoregulation (10 minutes)

Once established, bilateral TCD, blood pressure, ECG and end-tidal CO₂ will be acquired simultaneously for 5 minutes after a minimum of 5 minutes of supine rest. Continuous systolic, diastolic and mean values will be derived and related to each other by transfer function analysis using in-house software written in Matlab. This allows estimation of baroreceptor sensitivity and cerebral autoregulation.

CO₂ reactivity (10 minutes)

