Following the period of monitoring, reactivity to CO₂ will be assessed by 3 minutes of inhalation of 6% CO₂, delivered via a respiratory circuit with a non-invasive ventilation mask and harness, supplied with 2 alternating periods of medical air versus 6%CO₂/21%O₂/balance N₂. The resulting increase in MCA mean flow velocity on TCD will be related to the change in end-tidal CO₂ to determine the vasodilatory response, adjusted for any change in blood pressure. Secondly, the participant will be instructed to hyperventilate at 1 breath per second for 30 seconds to reduce etCO₂ and estimate change in mean flow velocity per unit change in etCO₂.

Peripheral Vascular Reactivity (10 minutes)

Effects of medication on peripheral endothelial function will be estimated by assessment of flow-mediated slowing (Vicorder, Skidmore Industries). This determines the change in speed of flow of the pressure waveform between two sites in the arm, before and after a short period of occlusion. This induces endothelium dependent vasodilatation, which results in slowing of the speed of blood flow. If the previous tests last >60 minutes to achieve accurate measurements, or if the participant finds this procedure too uncomfortable this element may be omitted at follow up visits.

Blood pressure monitoring

Patients will be provided with a home blood pressure monitor to record their blood pressure twice daily (on waking and evening), recorded three times at each sitting, for 7 days prior to their subsequent study visit (A&D UA-767 BT). Patients will be asked to record their blood pressure readings and return them for

assessment of how allocated treatment affects blood pressure, and how this may interact with the primary outcome measure. If potential symptoms of hypotension occur, patients may be requested to perform additional readings for clinical safety purposes. Participants will be asked to record any side-effects on the same diary card as used for blood pressure monitoring.

Medication Dispensation

Study medication / placebo will be dispensed by the Oxford University Clinical Trials Pharmacy after randomisation.

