2.1.3 Tertiary outcome measures

- a) Systolic and diastolic blood pressure will be measured as the mean of the second two readings at each sitting from day 2 to the last day of measurement
- b) Beat-to-beat variability in systolic blood pressure will be measured over 5 minutes as the coefficient of variation (standard deviation / mean) after automated and manual removal of artefacts and after removal of any linear trend in the data.
- c) Flow mediated slowing will be measured as the absolute reduction in speed of flow from the average value during baseline to the minimum valid reading during the first 30 seconds of recovery (assessed blind).
- d) Indices of resting state cerebral autoregulation (transfer function analysis derived gain, phase and coherence) will be determined by transfer function analysis according to the

protocol recommended in the CARNET White Paper, using the open access tfa script developed by [name] and made available via the CARNET collaboration.

- e) A voxel-wise general linear model based analysis of cerebrovascular reactivity on MRI will be performed with the FEAT.
- f) Estimates of CVR will be determined from the peak velocity achieved during each test (hyperventilation, 4% CO₂ and 6% CO₂) minus the baseline value, divided by the peak minus baseline etCO₂ values. Results will be expressed both as absolute and percentage change in mean velocity per mmHg change in etCO₂.

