5.2 Secondary outcomes

The percentage change in mean blood flow velocity per mmHg during inhalation of air, 4% and 6% carbon dioxide versus medical air estimated from the beta-coefficient from a phase-shifted linear regression will be compared between sildenafil and placebo treatment by paired t-test and a 95% confidence interval if normality distribution assumptions hold, or the non-parametric Wilcoxon signed rank test. The analysis will be re-run using the PP population as a sensitivity analysis, and using the percentage change from baseline.

A non-inferiority analysis will be based on the 95% CI for the mean change difference between sildenafil and cilostazol. If the upper 97.5% confidence limit is less than 0.08 units (=inferiority margin, 2/3 of the clinically estimated overall cilostazol effect), non-inferiority will be declared. The data will be transformed if normality assumptions do not hold. The PP population will be used for this analysis, with the ITT population being used in a sensitivity analysis.

Differences in reactivity to CO₂ from baseline in each of three states (sildenafil, cilostazol, placebo) will be compared by mixed-effect general linear models, with post-hoc pairwise comparison, using the ITT population with the PP population being used in a sensitivity analysis. This will apply to both TCD measures of CO₂ reactivity and by ROI on MRI. On MRI, these analyses will also be performed on a voxel-wise basis by use of the FLAME tool (FSL).

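### Protocol 8.5 promises blood-pressure adjustment of CO2 reactivity on TCD, but SAP 2.1.2 uses an unadjusted slope, so a treatment difference in the pressure response to CO2 can be counted as a change in reactivity

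*SAP*

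**What the plan says.** Protocol 8.5, under CO2 reactivity, relates the increase in MCA mean flow velocity to the change in end-tidal CO2 (etCO2) "to determine the vasodilatory response, adjusted for any change in blood pressure".

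SAP 2.1 points back to that section: "A detailed description of the physiological assessment measures is provided in the protocol (sections 8.5 & 8.6"). SAP 2.1.2 then says that the TCD measure "will be estimated by the unstandardized beta-coefficient from an unadjusted linear regression between the end-tidal" CO2 and MCA mean velocity, after a time shift of the etCO2 trace. The one sensitivity analysis attached to the measure is: "A sensitivity analysis will be performed using the standardised beta-coefficients for increase in blood flow velocity per increase in end-tidal" CO2.

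SAP 5.2 carries this measure into two comparisons. For sildenafil against placebo, the percentage velocity change per mmHg "estimated from the beta-coefficient from a phase-shifted linear regression will be compared between sildenafil and placebo treatment by paired t-test" (or Wilcoxon). Across the three treatments, differences in reactivity "will be compared by mixed-effect general linear models, with post-hoc pairwise comparison, using the ITT population". The alternative reactivity estimates in SAP 2.1.3(f) take peak velocity "minus the baseline value, divided by the peak minus baseline" etCO2.

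The protocol is not uniform. Its Synopsis and its section 5 table describe the outcome as a velocity change under CO2 and do not mention pressure. Protocol 11.1 names no pressure covariate for the reactivity comparison.

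**The concern.** MCA velocity can rise during CO2 inhalation because the distal vessels dilate or because arterial pressure rises. Protocol 8.5 says the aim is the vasodilatory response and that pressure change will be adjusted for. A slope on etCO2 alone combines both components. The study drugs are chosen as vasodilating agents, so a different pressure response to CO2 on drug and on placebo is possible. If it occurred, it would not cancel in the within-person contrast.

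At stake is the interpretation of secondary objective 1 and of the three-treatment reactivity model. A drug that only blunts or enlarges the pressure rise could appear to change cerebral reactivity, or a real change could be masked. Anyone reading both documents also finds two definitions of one secondary outcome, with no statement of which governs.

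**Working it through.** **1. The texts side by side**

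| Place | Pressure term in TCD reactivity? |
|---|---|
| Protocol 8.5, CO2 reactivity | Yes, no model given |
| Protocol Synopsis and section 5 | Not mentioned |
| Protocol 11.1, secondary outcome | Not mentioned |
| SAP 2.1.2, main measure | Explicitly unadjusted |
| SAP 2.1.2, standardised-beta sensitivity analysis | None |
| SAP 2.1.3(f), alternative estimates | None |
| SAP 5.2, paired test, mixed model, per-protocol and percentage-change re-runs | None |

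The nearest analysis elsewhere is a tertiary one in Protocol 11.1. It relates indices such as home blood pressure and blood pressure variability to pulsatility and reactivity. None of those indices is the pressure change during CO2 inhalation.

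**2. What the unadjusted slope estimates**

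The plan states no figure for CO2 reactivity, so there is none to reproduce. Its sample sizes concern MCA-PI. Write velocity as a percentage of its baseline value:

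- v = a + c × etCO2 + p × MAP, where MAP is mean arterial pressure and c is the response at fixed pressure
- MAP = m + d × etCO2, where d is the pressure response to CO2

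The regression on etCO2 alone has slope c + p × d. If p is the same on both treatments, the treatment difference in that slope is Δc + p × Δd. The artefact is p × Δd and is zero when Δd = 0.

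**3. Size, on assumed inputs only**

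The documents give neither p nor Δd. Assume p = 0.3 to 1.0 % per mmHg MAP, Δd = 0.1 to 0.4 mmHg MAP per mmHg etCO2, and a reactivity of 2 to 4 % per mmHg.

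- Low end: 0.3 × 0.1 = 0.03 % per mmHg; 0.03/4 is about 1% of reactivity
- High end: 1.0 × 0.4 = 0.40 % per mmHg; 0.40/2 = 20% of reactivity

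A simulation of the air, 4% CO2, air, 6% CO2 sequence gives a second illustration. It assumes c = 2.5 % per mmHg, d = 1 on placebo and d = 0.5 on drug, with c unchanged:

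| p | Unadjusted, placebo | Unadjusted, drug | Spurious difference | Adjusted, both |
|---|---|---|---|---|
| 0.2 | 2.70 | 2.60 | -0.10 | about 2.50 |
| 0.5 | 3.00 | 2.75 | -0.25 | about 2.50 |
| 1.0 | 3.50 | 3.00 | -0.49 | about 2.50 |

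**4. A steady fall in resting pressure is different**

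With MAP 8 mmHg lower throughout and d unchanged, the fall goes mainly into the intercept. The percentage slope moves only because baseline velocity is lower: at p = 0.5 the baseline is 100 - 0.5 × 8 = 96, and 3.00/0.96 = 3.125, a rise of about 0.12. The simulated rises are 0.04, 0.12 and 0.31 for p = 0.2, 0.5 and 1.0. A within-session pressure covariate does not remove this part: at p = 0.5 the adjusted slope becomes 2.5/0.96 = 2.60.

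**5. Is pressure available?**

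Protocol 8.5 states simultaneous recording of TCD, pressure and etCO2 for the resting period, and places the CO2 test after that period. Its TCD paragraph says "All waveforms will be simultaneously acquired with a AD Instruments Powerlab 8/35", and an adjustment for pressure presupposes a recording. For the TCD CO2 test, pressure recording is therefore implied but not stated. Protocol 8.7 states it outright only for the MRI challenge.

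**The case against.** Four points have force.

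- **The protocol does not speak with one voice.** A reader might infer that the SAP abandons the protocol's definition of the outcome. Only the procedural text in 8.5 mentions adjustment; the Synopsis and section 5 do not, and the SAP's unadjusted slope agrees with them on this. What stands is an unreconciled conflict.
- **Bias is not automatic.** A reader might infer that any drug effect on blood pressure is counted as reactivity. Step 4 shows otherwise: the pressure response during inhalation has to differ. The protocol's plan to study treatment effects on blood pressure concerns a week of home readings and their interaction with the primary outcome, so it is no evidence of such a difference.
- **Adjustment is a choice of target.** A reader might infer that the adjusted slope is the only correct one. Pressure during CO2 is measured after treatment and may carry part of the drug's effect. The stated objective is whether sildenafil alters reactivity, without requiring a pressure-independent effect. An unadjusted total effect is legitimate if it is declared.
- **Feasibility and size are not established.** Pressure recording during the TCD test is only implied, and the lower end of the assumed range may be negligible. The documents give no SD for reactivity against which to judge it.

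None of this explains why the SAP drops an adjustment promised in the section it cites, or supplies an analysis that would reveal a pressure artefact.

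**Conclusion.** The concern holds in a limited form. The conflict between Protocol 8.5 and SAP 2.1.2 is plain on the page, and the SAP neither repairs nor justifies it. The statistical consequence is conditional: a difference between treatments in the pressure response to CO2 can be counted as a difference in reactivity.

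The ranges in the working rest wholly on assumed coefficients and, in the algebra, on a common pressure-to-velocity relation across treatments. They show that the artefact could be trivial or could matter; they do not predict it. The issue is confined to TCD CO2 reactivity in secondary objective 1 and the three-treatment model. The primary MCA-PI analysis and the sample size do not depend on it. It should be settled before unblinding, but it does not threaten the trial's main conclusion.

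**What to change.** Before unblinding (the SAP history records version 0.5 as preceding it):

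1. Reconcile Protocol 8.5 with Protocol section 5 and SAP 2.1.2, and state whether the target is the total CO2 response or the response independent of pressure.
2. In SAP 2.1.2, pre-specify the etCO2 coefficient from a regression that also contains concurrent mean arterial pressure, and say how the pressure trace is aligned with the time-shifted etCO2 trace. Report it beside the unadjusted slope.
3. In SAP 5.2, carry the adjusted slope through the sildenafil-placebo test and the three-treatment model. Make it the main measure if Protocol 8.5 is to stand. Otherwise name it as a sensitivity analysis and justify the departure.
4. Confirm that pressure was recorded during the TCD CO2 test. State whether a visit without a usable trace leaves the adjusted comparison or how else it is handled, so that adjusted and unadjusted slopes are not mixed within a pair unnoticed.

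The cost is SAP wording and one more regressor. If the traces exist, no new data are needed. Pressure and etCO2 are correlated, so single-visit slopes will be somewhat noisier, and some visits will have only the unadjusted value.
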